# AIM 1: Determine the impact of timed rectal evacuation on anorectal dysfunction in MS patients

We will conduct a four week, single-center, randomized, double-blind placebo controlled clinical trial designed to assess the efficacy of timed rectal evacuation in improving the subjective global assessment of bowel symptoms in a cohort of patients with mild-to-moderate severity MS disease. Patients will be randomized 1:1 to administer either placebo or bisacodyl 10 mg rectal suppositories every other day during the 4 week trial. The primary endpoint will be the change in patients' rating of bowel symptom severity (10 point rating scale) at end of 4 weeks compared to baseline values. We will define an adequate treatment response as greater than a 30% reduction in symptom severity using an intention-to-treat analysis.

AIM 2: Determine the predictors of treatment response and impacts on quality of life

We plan to collect information on the patients' assessed severity of baseline and treatment-associated anorectal dysfunction, their impact on quality of life, as well as daily bowel diaries. Patients also will undergo anorectal sensory and manometric testing as a part of their routine clinical care. Enrolled patients that complete the study will be assessed for study medication compliance. All of these measures will be used to explore factors that are associated with treatment response. Changes in assessments of anorectal dysfunction-related quality of life will serve as key secondary end-points.

This proposal will significantly advance MS care and management by developing the evidence to support the adoption of a simple, safe, and cost-effective clinical treatment algorithm for anorectal dysfunction in the MS population. This paradigm for anorectal dysfunction management could be applicable to a majority of MS patients, and the treatment algorithm could be introduced to patients by nurses or mid-level clinical providers during points of routine MS patient care. Importantly, the treatment could be effectively accomplished by most patients and their caregivers at home. The findings of this investigation could also have a broader influence on care models for anorectal dysfunction associated with a range of other neurological illnesses, such as Parkinson's Disease, ALS, or stroke.

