RESEARCH PLAN: The goal of this proposal is to determine the efficacy of timed rectal evacuation as a treatment for anorectal dysfunction symptoms in patients with mild-to-moderate severe MS. The primary end-point of the randomized clinical trial is a greater than 30% improvement in patients' subjective global assessment of bowel symptom severity after 4 weeks. In secondary analyses, we will determine the factors predicting treatment response, as well as assess the impact of therapy on measures of global and anorectal dysfunction-related quality of life.

Study Design: This is a single-center, randomized, double-blind placebo controlled trial incorporated into routine clinical care for MS patients with anorectal dysfunction. Patients will be randomized to receive placebo or bisacodyl 10 mg rectal suppositories every other day for 4 weeks.

Study Population and enrollment: Patients at the University of Pittsburgh Medical Center (UPMC) MS Center with anorectal dysfunction will be recruited via either an existing registry, chart review, and/or ongoing care encounters. The UPMC MS Center currently cares for well over 2,000 patients. The study is adequately powered if enrollment reaches 56 patients (see Power Analysis below). To ensure adequate numbers in an intention-to-treat analysis, we will plan for a ~20% patient drop-out rate (thus, enrolling 70 patients in total). Normal clinical care pathways at UPMC naturally generate ~2-3 patient consultations per week for MS patients with anorectal dysfunction (total ~125 patients per year), and the pool of potential study candidates far exceeds that number. Therefore, enrollment of 70 patients appears quite feasible.

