Finally in Phase 3, after the 4 week study period, patients will meet with the study coordinator to collect unused study medication and completed bowel diaries, and then undergo final reassessments of bowel dysfunction severity and QOL measures. This process could take up to 1 hour. After the questionnaires are completed, patients and the PI/Co-PI will be debriefed (i.e. study arm allocation will be revealed) before having a routine followup clinic visit (continuity of care).

- 1) The study coordinator will identify and screen potential study subjects (by accessing the "UPMC Multiple Sclerosis and Related Disorders Registry" (PRO12010609) to identify prospective subjects), coordinate the informed consent process with the PI/Co-PI, collect intake questionnaires, and provide instruction on bowel diaries (Phase 1). The coordinator will schedule referrals for anorectal function testing and follow-up DDC visit, and contact patients during the 4-week trial period to verify compliance. Finally, the coordinator will collect bowel diaries and remaining medications at study end, administer study exit questionnaires, and then debrief subjects and the PI/Co-PI once the blind is broken (Phase 3).
- 2) DDC GI nursing staff routinely performs HRAM studies and will do so in this study. The PI/Co-PI will be involved in clinical care and recommendations both during Phase 2 and Phase 3 (and beyond).
- 3) MS Physicians will be involved in initial identification of potential subjects and all MS-related continuity of care.
- 4) Falk Pharmacy serves UPMC for clinical trials, and staff will ensure the 1:1 randomization and distribution of either twenty placebo or biscodyl 10 mg rectal suppositories (used every other day over 4 weeks during the study period). Falk Pharmacy staff is experienced in running clinical trials and maintaining double-blind study conditions between subjects and investigators. Patients will receive a slight excess number of suppositories in order to assess study medication compliance at trial end.

STUDY MEASURES: We plan to obtain the following information from all enrolled patients:
1) Primary Patient-Reported Outcome Measure: "Using a scale of 1 to 10 (1 being no problem and 10 being maximally impactful symptoms), how would you rate the severity of your bowel symptoms over the past 2 weeks?"

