### **Study Flow Chart:**

Name	Modified Date
STUDY DIAGRAM - UPDATED 10-26-15.pdf	10/26/2015 11:13 AM

[reviewer notes¬]

2.7 Will follow-up procedures be performed specifically for research purposes? Follow-up procedures may include phone calls, interviews, biomedical tests or other monitoring procedures.

\* No

[reviewer notes¬]

2.8 Does this research study involve the use of any questionnaires, interview or survey instruments?

\* Yes

Upload a copy of all materials except for the SCID or KSADS which are on file at the IRB. The use of all instruments must be addressed in question 2.6 and/or question 2.7 (except for an exempt submission where they should be addressed on the appropriate uploaded exempt form).

Name	Modified Date
Primary Endpoint - PAC-SYM and FISI Questionnaires.pdf	11/3/2015 3:24 PM
SF-36 QUESTIONNAIRE in PDF.pdf	11/3/2015 3:24 PM
FIQL .pdf	11/3/2015 3:24 PM
PAC-QOL.pdf	11/3/2015 3:23 PM
Bowel Diary Pages.pdf	11/3/2015 3:35 PM

Previously the name and publisher for commercially available materials were listed in the textbox below but effective 9/1/2015, all materials (except for the SCID and KSADS) must be uploaded using the Add button above.

Each of these questionnaires (PAC-SYM, FISI, PAC-QOL, FIQL, SF-36) are open access.

[reviewer notes¬]

2.9 If subjects are also patients, will any clinical procedures that are being used for their conventional medical care also be used for research purposes?

\* yes

If **Yes,** describe the clinical procedures (and, if applicable, their frequency) that will be used for research purposes:

Anorectal function testing (anorectal sensory function and high resolution anorectal manometry [HRAM]) is commonly used for to help patients with anorectal dysfunction. The testing is typically performed once.

**2.10** The blood sample question was moved to 2.6.1.

[reviewer notes¬]

- 2.11 What is the total duration of the subject's participation in this research study across all visits, including follow-up surveillance?
  - Up to 8 weeks

[reviewer notes¬]

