- 2.14.2 Are you requesting a waiver of the requirement to obtain written HIPAA authorization for the collection of the PHI?
  - \* No

[reviewer notes-]

- 2.15 Does this research study involve the long-term storage (banking) of biological specimens?
  - \* No

[reviewer notes¬]

- 2.16 Will research participants be asked to provide information about their family members or acquaintances?
  - \* No

[reviewer notes¬]

2.17 What are the main outcome variables that will be evaluated in this study?

PRIMARY END POINT: The primary end-point of the randomized clinical trial is a greater than 30% improvement in patients' subjective global assessment of bowel symptom severity after 4 weeks based on the answer to the following question: "Using a scale of 1 to 10 (1 being no problem and 10 being maximally impactful symptoms), how would you rate the severity of your bowel symptoms over the past 2 weeks?"

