3.8 Does this research study involve neonates of uncertain viability or nonviable neonates?

\* No

[reviewer notes¬]

- 3.9 Fetal Tissues: Does this research involve the use of fetal tissues or organs?
  - \* No

[reviewer notes¬]
--->

3.10 What is the total number of subjects to be studied at this site, including subjects to be screened for eligibility?

Note: The number below is calculated by summing the data entered in question 3.11. Any additions or changes to the values entered in 3.11 will be reflected in 3.10.

- \* 400
- 3.11 Identify each of the disease or condition specific subgroups (include healthy volunteers, if applicable) that will be studied.

Click on the "Add" button and specify for each subgroup:

- 1) how many subjects will undergo research related procedures at this site; and
- 2) if applicable, how many subjects will be required to undergo screening procedures (e.g., blood work, EKG, x-rays, etc.) to establish eligibility. Do Not include subjects who will undergo preliminary telephone screening.

\*

Subgroup	Number to undergo research procedures	Number to undergo screening procedures
View MS patients	70	400

- 3.12 Provide a statistical justification for the total number of subjects to be enrolled into this research study at the multicenter sites or this site.
  - \* Described below:

The primary outcome measure is the group mean difference in subjective severity ratings of bowel symptoms using a 10 point scale. It is generally regarded that a 3-point reduction represents a clinically meaningful change using such a scale, and similar

Section: Section 3 - Human Subjects

research studies using patient-reported outcomes have reported standard deviations ranging around ~2.5 points on a 10 point scale. However, we do not have baseline data in this population to estimate variance, and thus we took a conservative estimate with an expected standard deviation of 4 points. Given these assumptions, we will need 28 patients in each study arm to detect at least a 3 point reduction in symptom severity, with a power of 0.80, alpha=P<0.05 in a two-tailed analysis.

Thus, the study is adequately powered if enrollment reaches 56 patients. However, to ensure adequate numbers in an intention-to-treat analysis, we will plan for a ~20% patient drop-out rate. Therefore, we will aim to enroll 70 patients in total.

[reviewer notes¬]

3.13 Inclusion Criteria: List the specific criteria for inclusion of potential subjects.

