If the subject withdraws from the study after having passed Phase 1 (i.e. baseline measures of bowel dysfunction and quality of life), we would keep the data for an "intention-to-treat" analysis (with the assumption of an non-response). If a subject has not completed Phase 1, then the research data will be destroyed.

**5.17** Following the required data retention period, describe the procedures utilized to protect subject confidentiality. (e.g., destruction of research records; removal of identifiers; destruction of linkage code information; secured long-term retention)

We will destroy primary research records with any identifiers, but may opt to retain deidentified electronic data on a secured server for future re-analysis. Per University of Pittsburgh guidelines, research records will be archived for a minimum of seven years after final reporting or publication of a project.

Section: Section 6 - Costs and Payments

[reviewer notes-]

6.1 Will research subjects or their insurance providers be charged for any of the procedures (e.g., screening procedures, research procedures, follow-up procedures) performed for the purpose of this research study?

Yes; charges will be billed only for procedures performed as part of the subject's routine clinical care as addressed in question 2.9

[reviewer notes-]

6.2 Will subjects be compensated in any way for their participation in this research study?

\* No

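### Withdrawals after Phase 1 are scored as non-response and no step seeks their week-4 rating, so up to 14 of 70 primary outcomes could be assumed rather than observed

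*Combined protocol and SAP*

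**What the plan says.** Section 5.16 is the only place that says what happens to the outcome of a patient who leaves. After Phase 1, the data are kept for an intention-to-treat "analysis (with the assumption of an non-response"). Before Phase 1 is complete, the data are destroyed.

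Sections 2.6 and 3.12 expect a sizeable number of leavers: "we will plan for a ~20% patient drop-out rate", which takes 56 patients to 70.

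The final rating is taken at the Phase 3 meeting with the coordinator (section 2.6). During treatment the coordinator will also "contact patients during the 4-week trial period to verify compliance", and section 5.1.1 adds contact to check for problems. Neither section mentions collecting the outcome from someone who has withdrawn. Section 2.7 answers No to research follow-up procedures; the form's own prompt reads "Follow-up procedures may include phone calls, interviews, biomedical tests or other monitoring procedures".

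The primary endpoint is defined in two ways. Section 2.17 has "a greater than 30% improvement in patients' subjective global assessment of bowel symptom severity after 4 weeks". Section 3.12 says "The primary outcome measure is the group mean difference in subjective severity ratings of bowel symptoms using a 10 point scale". Section 2.18 names Fisher's exact test, t-tests and logistic regression, and gives no missing-data method or sensitivity analysis.

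On compliance, Aim 2 in section 1.2 says "Enrolled patients that complete the study will be assessed for study medication compliance", whereas the Study Measures list in section 2.6, which includes compliance, opens "We plan to obtain the following information from all enrolled patients".

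**The concern.** Assumed non-response turns leaving the study into a treatment failure, whatever happened to the patient's symptoms. The plan itself gives a reason to doubt that leavers have no response. Section 5.12 expects most patients, including those on placebo, to improve somewhat because all are advised on oral treatment for stool form. A patient who leaves may keep taking that treatment and improve.

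If the arms lose different numbers of patients, for instance through local side effects on bisacodyl or lack of effect on placebo, the difference in leaving is carried into the difference in response. If they lose equal numbers, a real difference can be diluted.

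For the mean comparison in section 3.12 the rule is incomplete: a non-response is not a score. The analyst would have to choose a value, or drop the patient, after the data are in.

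**Working it through.** **Inputs from the documents.** 1:1 allocation (section 1.2). Difference 3 points, SD 4, two-sided alpha 0.05, power 0.80, 28 per arm, about 20% drop-out, 70 enrolled (section 3.12). Hence 35 per arm and 0.20 × 70 = 14 leavers.

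**The plan's own figures.** n per arm = 2 × (1.96 + 0.84)² × 4² / 3², which rounds up to 28; power at 28 is 80.1% (normal approximation). 56 / 0.80 = 70. Both reproduce. The 80% therefore describes 56 observed patients, not 70 patients of whom 14 are assigned an outcome.

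**Responder endpoint.** Let a and b be the exits on active and placebo, and r the response rate the leavers would truly have had, taken as equal in both arms. Scoring them all as non-response shifts the active-minus-placebo difference by −r × (a − b) / 35.

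Assume 50% true response in everyone, so the true difference is zero:
- Exits 7:7: 14/35 against 14/35, or 40% against 40%.
- Exits 9:5: 26 × 0.5 / 35 = 37.1% against 30 × 0.5 / 35 = 42.9%.
- Exits 10:4: 25 × 0.5 / 35 = 35.7% against 31 × 0.5 / 35 = 44.3%, a shift of 8.6 points.

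The shift depends on r. For the 10:4 split it is 6 × r / 35: 8.6 points at r = 50%, 4.3 points at r = 25%, and zero at r = 0.

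Equal exits also matter if leavers would have responded like completers in their own arm. With assumed true rates of 65% and 30% and 20% imputed in each arm, the rates become 0.8 × 65% = 52% and 0.8 × 30% = 24%. The difference falls from 35 to 28 points, and Fisher's exact power at 35 per arm falls from 76.9% to 60.2%.

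**Mean difference.** The plan defines no value, so this needs a further assumption: non-response means zero change. With 20% imputed in each arm the 3-point effect becomes 3 × 0.8 = 2.4. At 35 per arm and SD 4, power is 70.9%. If the variance reflects the mixture of zeros and observed changes, it is 73 to 78%, for a placebo change of 2 down to 0 points.

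If every leaver were rated and responded like completers in the same arm, power would be 88.1%. If active-arm leavers responded like placebo patients, the true effect would itself be 2.4 and power would stay at 70.9%.

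**The case against.** Counting withdrawal as non-response is a common rule for a responder endpoint. If leavers truly do not respond, it gives the right answer. The largest shift shown, 8.6 points, corresponds to three patients in 35. It is smaller than one standard error of the difference, √(2 × 0.4 × 0.6 / 35) = 11.7 points at a 40% response. All of this stands. What it does not answer is why the rule should apply before anyone has tried to obtain the rating.

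A reader might also infer more than the documents support:
- That every patient who stops the suppositories is scored a failure. Section 5.16 covers only withdrawal from the study. It does not equate stopping treatment with withdrawal, and nothing bars a patient off treatment from being rated at Phase 3. The plan is silent, which is why it needs a definition.
- That section 2.7 forbids a phone call. Sections 2.6 and 5.1.1 already plan coordinator contact during treatment, so the No cannot bar calls altogether and may refer to follow-up after Phase 3.
- That 8.6 points is a false difference the trial will show. It holds only if leavers would have responded like completers, and the 10:4 split is assumed.
- That the secondary scales will be analysed in completers only, or that compliance will be materially overstated. Section 2.18 does not say the first. The compliance mismatch is a minor inconsistency of wording, and the documents give no dose-use figures from which to size it.

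A phone call is not a complete remedy either. It reaches only patients who allow contact, and it fills neither the secondary questionnaires nor the mean for patients who cannot be reached.

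**Conclusion.** The point holds. A stated rule assigns the outcome of everyone who withdraws after Phase 1, the plan expects about 20% drop-out, and no section plans to ask leavers for a rating that is one question long. That no outcome is sought is read from the absence of any such step; the documents do not say so outright.

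Up to 14 of 70 primary outcomes are exposed. The number is an upper figure, because some patients counted as drop-outs may still give a rating and some may leave before Phase 1 is complete. The resulting bias is zero if leavers would not have responded. It reaches 8.6 points with 50% true response in everyone and a 10:4 split. Response rates, exit splits and zero change for leavers are assumptions, not figures from the plan.

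Separately, the rule leaves missing values undefined for the mean difference in section 3.12, and the two definitions of the primary endpoint must be reconciled. Replacing an assumption with an observation is the certain benefit; a gain in power depends on how leavers actually respond.

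**What to change.** 1. In sections 5.16 and 2.6, state that stopping the suppositories is not withdrawal from the study and that such patients are still rated at Phase 3.
2. For patients who received study drug, will not attend Phase 3 but allow contact, have the existing coordinator obtain the 1 to 10 rating by phone at the scheduled week-4 time, before unblinding. Use that rating in the intention-to-treat analysis. A rating at the moment of exit is no substitute: the question looks back two weeks, so an early exit rating would mix baseline with treatment.
3. Keep assumed non-response only where no week-4 rating can be obtained, and add a sensitivity analysis of that assumption to section 2.18.
4. State how patients who leave between Phase 1 and dispensing are handled. Study drug is given at the end of Phase 2, so the present rule includes people who never received it.
5. State the value or method used for missing ratings in the mean comparison.
6. Align the compliance population in Aim 2 with Study Measures, and bring the answer in section 2.7 into line with the planned contacts.

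The cost is protocol and consent wording and a short call to each of at most about 14 patients. Some ratings will come by phone. Leavers' week-4 ratings may reflect treatment taken after exit, since section 5.1 notes that bisacodyl is available over the counter.

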## 7.2 Indicate all sources of support for this research study.

\*

### Selections

Foundation: Upload a copy of the research plan that was submitted to the agency

If **Federal** support, provide the sponsor information:

Federal sponsor Grant Title Grant number Awardee institution Federal grant application

For projects not supported by a federal grant, upload the research plan that was submitted for funding:

Name Modified Date

PilotResearch Guidelines ApplicationForm June 2015 - [name] .pdf 10/26/2015 1:13 PM

If **Industry** support, provide the sponsor information and level of support:

If **Foundation** support, provide the sponsor information: Consortium of Multiple Sclerosis Centers (CMSC)

If **Other** support, provide the support information and level of support:

[reviewer notes¬]

# 7.3 Is this study funded in part or whole by a PHS Agency?

# Does any investigator\* involved in this study (select all that apply):

	Name
	A. Have equity in a publicly-traded entity that either sponsors** this research or owns the technology being evaluated or developed that exceeds a 5% ownership interest or a current value of \$10,000 ?
	B. Have equity in a non-publicly-traded entity that either sponsors this research or owns the technology being evaluated or developed?
	C. Receive salary, consulting fees, honoraria, royalties or other remuneration from an entity that either sponsors this research or owns the technology being evaluated or developed that is expected to exceed \$10,000 during the past or next 12 months?
	D. Have rights as either the author or inventor of intellectual property being evaluated or developed in this research that is the subject of an issued patent or has been optioned or licensed to an entity?
	E. Have an officer or management position**** with a Licensed Start-up Company overseen by the COI Committee that either sponsors this research or owns the technology being evaluated or developed?
	F. Receive compensation of any amount when the value of the compensation would be affected by the outcome of this research, such as compensation that is explicitly greater for a favorable outcome than for an unfavorable outcome or compensation in the form of an equity interest in the entity that either sponsors this research or owns the technology being evaluated or developed?
V	None of the above options apply and there are no other financial conflicts of interest in the conduct of this research.
rega as w	restigator means the PI, co-investigators, and any other member of the study team, rdless of title, who participates in the design, conduct, or reporting of this research, ell as his/her spouse, registered domestic partner, dependents, or other members of the study team,

\*\*through the provision of funds, drugs, devices, or other support for this research

relevant members of the study team review the above questions describing

\*\*\*\*Such as serving on the Board of Directors or Board of Managers or a position that carries a fiduciary responsibility to the company (e.g., CEO, CFO, CTO, or CMO).

Section: Supporting Documentation

[reviewer notes¬]

